### **Exclusion criteria:**

1. ASA > II
2. Hemodynamically unstable
3. Disease affecting neuromuscular transmission (myasthenia gravies ...etc.)
4. GCS < 15.
5. Any cardiac patient (ischemic heart disease – cardiomyopathy...etc.)

### **Methodology in details :**

Before induction of anaesthesia and Before Rocronium administration, the baseline twitch response will be established with a neuromuscular nerve stimulator (NMT mechanosensor, GE healthcare, Helsinki, Finland) to achieve the maximum response of the adductor pollicise muscle.

The maximum electromyography amplitude of T1 before Rocronium administration will be considered to be the control response (Tc). The response of the adductor pollicise brevis muscle to TOF stimulation of the ulnar nerve will be monitored every 5 min and will be recorded every 30 min, and the infusion dose of Rocronium will be adjusted according to the target of the partial NMB group.

Anaesthesia will be induced by I.V. propofol (1.5-2 mg/kg) with fentanyl (2–4 mcg/kg) through syringe infusion pump. After induction, tracheal intubation will be facilitated with Rocronium (0.6 mg/kg).

Anaesthesia will be maintained by propofol and fentanyl infusions through the pump. Subjects will be randomly allocated into one of the two groups:

Group A (n=20): will receive Rocronium as muscle relaxant, maintain partial NMB T2/TC 0.5 or TOF count 2 (10) , Fentanyl will be infused at a dose range of 0.5–1mcg/kg/hr. to control the haemodynamic response to the surgical procedure within a 20% range of its preoperative value, and propofol will be infused at a dose range of 6–8 mg/kg/hr. to targeting Bispectral index at 40 -60.(11)

Group B (n=20): will not receive muscle relaxant, Fentanyl will be infused at a dose range of 0.5–1mcg/kg/hr. to control the haemodynamic response to the surgical procedure within a 20% range of its preoperative value, and

propofol will be infused at a dose range of 8–12 mg/kg/hr. to targeting Bispectral index at 25-35, after ending of monitoring of neurophysiology propofol dose will be dropped to 4–6 mg/kg/hr. targeting Bispectral index 40- 60.(11)

The mean arterial pressure during the surgery will be monitored every 5 min and will be recorded every 30 min and will be compared between the groups. Hypotension will be defined as a decrease in the mean arterial pressure of more than 20% of the preoperative value or below 55 mm Hg and will be treated by repeated 5 mg I.V. ephedrine bolus doses. Vasopressor infusion (norepinephrine in starting dose of 0.3 up to 2 mcg/kg/min) will be given if three or more ephedrine bolus doses is required. If bradycardia (60 beats min) developed, 0.6 mg of atropine will be administered.

Intraoperative monitoring included continuous ECG, pulse oximetry, arterial pressure (via arterial line and non-invasive arterial pressure cuff) ,temperature to avoid hypothermia ,The monitoring of transcranial electrophysiology for surgery will be performed by recording MEP, bispectral index (Covidien, Aspect medical systems, inc, Norwood, USA ) and train of four.

TCMEP monitoring of the facial nerve will be performed using two stimulant corkscrew scalp electrodes (NIM Eclipse, Midtronic) placed at positions C3 and C4 (International 10–20 EEG electrode system) Potentials will be recorded from paired sub dermal needle electrodes placed in the orbicularis oris and oculi . intraoperative monitoring for all patient will be performed by a same operator .

TCMEP recording will begin (1) prior to skin incision as baseline amplitude before muscle relaxant be taken for intubation (2) at Dural closure and end \start amplitude ratio will be calculated.

After the end of surgery, anaesthetic drugs will be stopped The extubation criteria are as follows: TOF ratio > 0.9, BIS > 70, regular respiratory pattern, tidal volume of at least 5 ml/kg and SpO2 > 95% when the patient breathes spontaneously.

The patient will be sent to the PACU while the neurosurgeons will assess appearance of neurological dysfunction.

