## **5. Objectives:**

This study is designed to compare the operating condition of two different levels of muscle relaxation on facial nerve monitoring using transcranial motor evoked potential in CPA surgery at KasrAlainy University Hospitals.

- To Estimate End to start facial nerve MEP amplitude ratio
- To determine the effect of neuromuscular relaxant degrees on recovery and hemodynamics.
- To compare doses of hypnotics given at different level of muscle relaxant.
- Assessment of propofol doses needed for enhancement of early recovery and ambulation.

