#### Measurement tools

1- Duration of the surgery from skin incision till skin closure will be recorded. And duration of anaesthesia from intubation till closure of anaesthetic agent.

2- TOFr and BIS will be monitored continuously every 5 min and will be recorded at baseline, at intubation, at skin incision, 30 and 60 minutes after skin incision, every 30min and 1 hr after extubation.

3- Intraoperative mean blood pressure and heart rate will be monitored every 5 min and will recorded in all groups immediately after induction, at surgical incision and every 30 minutes till the end of procedure.

4- Total amount of intraoperative propofol, fentanyl, ephedrine and norepinephrine consumption will be recorded

5- Number of hypotensive episodes, and required doses of ephedrine and vasopressors ( norepinephrine in starting dose of 0.3 up to 2 mcg/kg/min)

6- The eye-opening time (defined as the period from the cessation of propofol-fentanyl administration to when the patient opened his/her eyes on command)

7- Facial nerve function will be evaluated pre-operatively, immediately postoperatively.

8- Ratio of end operative to start-operative FMEP amplitude will be monitored .

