**Secondary outcome parameters (other outcomes to be assessed)**

1- Recovery profile ((time to eye opening, extubation, orientation, obeying commands, and an Aldrete score >9)) , [Time Frame: every 10 min for 1 hour at PACU.]

2- Total volume of propofol infused

3- BP , number of hypotension episodes and use of vasopressors

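### Bradycardia is foreseen and treated with atropine, but neither is listed for recording or reporting, and the half-hourly heart rates cannot stand in for them

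*Combined protocol and SAP*

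**What the plan says.** Section 5 makes haemodynamics an objective: "To determine the effect of neuromuscular relaxant degrees on recovery and hemodynamics".

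Methodology in details foresees two haemodynamic events that call for a drug. Hypotension is treated with ephedrine and then, if needed, norepinephrine. For the other event the text reads: "If bradycardia (60 beats min) developed, 0.6 mg of atropine will be administered". The rule is not restricted to one arm.

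The lists of what is collected treat the two events differently:

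- Measurement tools, item 3: "Intraoperative mean blood pressure and heart rate will be monitored every 5 min and will recorded in all groups immediately after induction", then at incision and "every 30 minutes till the end of procedure".
- Measurement tools, item 4: "Total amount of intraoperative propofol, fentanyl, ephedrine and norepinephrine consumption will be recorded".
- Measurement tools, item 5: "Number of hypotensive episodes, and required doses of ephedrine and vasopressors".
- Secondary outcome parameters, item 3: "BP , number of hypotension episodes and use of vasopressors".

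Hypotension therefore has an episode count, drug doses and a place among the secondary outcomes. Bradycardia and atropine appear in none of these lists. The available text describes no general collection of adverse events, and the entry on possible risk says that there is none.

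**The concern.** Methodology in details sets the arms apart in more than relaxant. Group A has propofol at 6–8 mg/kg/hr with a BIS target of 40–60. Group B has 8–12 mg/kg/hr with a target of 25–35 until neurophysiological monitoring ends. Whether the arms differ in bradycardia is a natural question under the haemodynamics objective.

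For blood pressure the plan guards against a familiar problem. Pressures recorded while hypotension is being treated can look alike in both arms, but the episode and dose counts still show which arm needed more treatment. For heart rate there is no such count. The only data are readings at fixed times, some of them taken under a drug given to raise the rate. If one arm has more bradycardia, the trial has no listed item from which to report it, and similar mean heart rates could be misread as evidence that the arms do not differ.

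**Working it through.** The plan states no heart-rate figure, so there is none to reproduce. The check has three steps.

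**1. The two events side by side**

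| | Hypotension | Bradycardia |
|---|---|---|
| Treatment stated (Methodology in details) | yes | yes |
| Underlying variable recorded (Measurement tools, item 3) | yes | yes |
| Treating drug totalled (item 4) | yes | no |
| Episodes and doses listed (item 5) | yes | no |
| Secondary outcome (item 3 of that list) | yes | no |

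Of the haemodynamic rescue drugs in Methodology in details, atropine is the only one missing from item 4.

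**2. What the scheduled readings can show**

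Checks are every 5 minutes and recordings after incision every 30. The share of checks recorded is 5/30 = 1/6, so an episode seen and treated at one of the other five checks need not appear in the study data.

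The size of this loss depends on figures that the documents do not give. The following is an illustration in which every input except the 5- and 30-minute intervals and the figure of 60 is assumed: between-patient SD 10 beats/min, within-patient SD 5, four hours of checks, atropine given at any check below 60, and a rise of 20 beats/min that fades linearly over 60 minutes.

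At each check, rate = patient mean + random variation + 20 × (1 − minutes since last dose/60), where the last term is zero before any dose and after 60 minutes. There were 40,000 simulated patients per arm.

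| Assumed untreated means | Untreated difference | Recorded difference | Any atropine | Any scheduled reading below 60 |
|---|---|---|---|---|
| 75 vs 70 | 4.9 | 3.3 | 36% vs 55% | 18% vs 32% |
| 72 vs 65 | 6.9 | 4.1 | 47% vs 73% | 26% vs 48% |
| 70 vs 60 | 10.0 | 5.6 | 55% vs 86% | 32% vs 65% |

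Share of atropine-treated patients with a scheduled reading below 60:

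- first row: 18/36 = 50% and 32/55 = 58%;
- second row: 26/47 = 55% and 48/73 = 66%;
- third row: 32/55 = 58% and 65/86 = 76%.

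So roughly a quarter to a half of treated patients would not be identifiable from the scheduled readings, while the rest would be. The recorded difference is 3.3/4.9 = 67%, 4.1/6.9 = 59% and 5.6/10.0 = 56% of the untreated one. With equal untreated means the arms receive atropine equally often on average, and there is no difference to shrink.

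**3. What a count could tell us with 20 per arm**

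Suppose one untreated value per patient with means 72 and 66 and SD 10 (assumed). The expected numbers below 60 are 20 × Φ((60 − 72)/10) = 20 × 0.115 = 2.3 and 20 × Φ((60 − 66)/10) = 20 × 0.274 = 5.5. The expected count per arm under no difference is (2.3 + 5.5)/2 = 3.9. That is below 5, so the exact test in Statistical analysis applies.

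Power is the sum, over all pairs of counts with a two-sided Fisher p-value below 0.05, of the product of the two binomial probabilities. It comes to about 15%. The count is therefore mainly descriptive.

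**The case against.** Four objections have weight.

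**The schedule does not select treated values.** A reader might infer that the trial records heart rate only after atropine. Item 3 of Measurement tools does not support that. Readings fall at fixed times whether or not atropine was given, so they include values before any dose, values in patients who never need it, and any low rate that coincides with a recording. Bradycardia is under-captured, not wholly lost.

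**Shrinkage is conditional.** A reader might also infer that every heart-rate comparison is pulled towards no difference. That follows only if the arm with the lower rate receives more atropine. Without a true difference there is nothing to dilute, and a large enough response to the drug could reverse the sign. Nothing in the documents says which arm, if either, will have more bradycardia.

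**The comparison is not a named one.** Methodology in details says that mean arterial pressure will be compared between groups and says nothing similar for heart rate, which is not a secondary outcome either. It is reached only through the broad haemodynamics objective and the general t test. Heart rate under care that includes rescue is also a legitimate quantity in its own right. For these reasons, and because the documents supply no heart-rate data, a claimed loss of power for a heart-rate test would have no basis here.

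**The doses may be on the anaesthetic chart anyway.** That is likely, but the plan does not make them study data, while it does so for the other rescue drugs.

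These objections limit the claim about bias. They leave the omission itself standing, since the plan's own handling of hypotension is the standard that it does not apply to bradycardia.

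**Conclusion.** The point holds as a gap in data collection and safety reporting. A foreseen, drug-treated event has no listed count and no listed drug total, so it cannot be reported by arm from the data the plan lists. The recorded heart rates do not fill the gap: after incision about one check in six is kept, and the kept values mix treated and untreated states.

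That mean heart rates may understate a difference is a possibility that depends on unequal atropine use. The illustrative sizes rest wholly on assumed rates, variability and drug response, and show direction and rough order only.

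The primary outcome, the sample size and the named secondary outcomes are untouched. This is a cheap improvement worth making, not a flaw that threatens the trial's main conclusion.

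**What to change.** 1. Measurement tools, item 4: add atropine to the drugs whose totals are recorded.
2. Measurement tools, item 5, and Secondary outcome parameters, item 3: add the number of patients with bradycardia as the protocol defines it, and atropine use.
3. So that the count is reproducible, the sponsor should state its intended definition in full. In the text available the figure of 60 carries no inequality sign, which may be a loss in conversion. The rule itself is for the sponsor to set.
4. Statistical analysis: report both items by arm, mainly descriptively. If a test is wanted, use the chi-square test, or the exact test where expected counts are below 5, as already planned.
5. State that mean heart rate alone will not be read as evidence on bradycardia.

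The cost is a few lines of text, one more entry taken from information the anaesthetic team already has, and one more secondary comparison with low power. It should be in place before data collection. Clinical management does not change.

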#### Measurement tools

1- Duration of the surgery from skin incision till skin closure will be recorded. And duration of anaesthesia from intubation till closure of anaesthetic agent.

2- TOFr and BIS will be monitored continuously every 5 min and will be recorded at baseline, at intubation, at skin incision, 30 and 60 minutes after skin incision, every 30min and 1 hr after extubation.

3- Intraoperative mean blood pressure and heart rate will be monitored every 5 min and will recorded in all groups immediately after induction, at surgical incision and every 30 minutes till the end of procedure.

4- Total amount of intraoperative propofol, fentanyl, ephedrine and norepinephrine consumption will be recorded

5- Number of hypotensive episodes, and required doses of ephedrine and vasopressors ( norepinephrine in starting dose of 0.3 up to 2 mcg/kg/min)

6- The eye-opening time (defined as the period from the cessation of propofol-fentanyl administration to when the patient opened his/her eyes on command)

7- Facial nerve function will be evaluated pre-operatively, immediately postoperatively.

8- Ratio of end operative to start-operative FMEP amplitude will be monitored .

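### Propofol, vasopressor and hypotension outcomes are compared as raw totals or counts, so anaesthesia time and body weight add avoidable noise to these secondary comparisons

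*Combined protocol and SAP*

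**What the plan says.** Measurement tools, item 4: "Total amount of intraoperative propofol, fentanyl, ephedrine and norepinephrine consumption will be recorded". Item 5 adds the "Number of hypotensive episodes, and required doses of ephedrine and vasopressors". The Secondary outcome parameters section carries these forward as "Total volume of propofol infused" and "BP , number of hypotension episodes and use of vasopressors". None has a denominator.

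The Statistical analysis section is generic: an unpaired t test for quantitative variables in two groups, and chi-square or an exact test for categorical ones. It names no offset, covariate or standardised form.

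Three other places matter:

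- Measurement tools, item 1, records both lengths of exposure: "Duration of the surgery from skin incision till skin closure will be recorded", and also "duration of anaesthesia from intubation till closure of anaesthetic agent".
- Methodology in details sets maintenance by weight and time. For Group A, "propofol will be infused at a dose range of 6–8 mg/kg/hr". Group B has 8–12 mg/kg/h during neurophysiological monitoring and 4–6 mg/kg/h afterwards. Fentanyl maintenance is also per kg per hour.
- Body weight is not among the listed measurements. It must be known to give doses such as "Anaesthesia will be induced by I.V. propofol (1.5-2 mg/kg) with fentanyl (2–4 mcg/kg"), but the plan does not say that it will be recorded.

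The Objectives section names a comparison of hypnotic doses between the two levels of relaxation, without a unit.

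**The concern.** A patient's propofol total is the infusion rate times weight times hours. The groups are defined by the rate, and the dose objective concerns the rate. Weight and case length are extra sources of spread that the planned comparison leaves in. Hypotensive episodes and vasopressor doses also accumulate with time under anaesthesia.

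Two things are at stake. A real difference in dosing or in the hourly frequency of hypotension may be missed because patients differ in size and length of operation. And a difference that is found cannot be read: more propofol in one group may mean a higher rate, longer cases or heavier patients. With 20 per arm, chance differences in mean duration are not negligible.

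**Working it through.** The plan states no figure for these outcomes, so there is none to reproduce. Its sample size concerns the MEP ratio only and does not enter here.

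**Inputs from the documents.** 20 per arm; unpaired t test; propofol 6–8 mg/kg/h in A, and 8–12 then 4–6 mg/kg/h in B.

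**Assumptions (not in the documents).** Duration mean 5 h, SD 1 to 2 h; weight mean 75 kg, SD 15 (CV 0.20); CV of the propofol rate within arm 0.15; test two-sided at 0.05.

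**1. A total can hide a rate.** For a 70 kg patient, 7 × 70 × 5 = 2450 mg and 10 × 70 × 3.5 = 2450 mg. The totals are equal, while the rates differ by 10/7 − 1 = 43%.

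**2. Spread of the total.** For independent factors, CV² = (1 + 0.15²)(1 + 0.20²)(1 + c²) − 1, where c is the CV of duration.

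- SD 1 h, c = 0.2: 1.0225 × 1.04 × 1.04 − 1 = 0.106, CV 0.325
- SD 1.5 h, c = 0.3: 1.0225 × 1.04 × 1.09 − 1 = 0.159, CV 0.399
- SD 2 h, c = 0.4: 1.0225 × 1.04 × 1.16 − 1 = 0.234, CV 0.483

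On mg/kg/h the CV is 0.15 throughout.

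**3. Power for a 25% rate difference.** Standardised difference d = 0.25 / (CV × √[(1 + 1.25²)/2]) = 0.25 / (CV × 1.132).

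| Scale | d | Simulated power |
|---|---|---|
| Total, SD 1 h | 0.68 | about 57% |
| Total, SD 1.5 h | 0.55 | about 40% |
| Total, SD 2 h | 0.46 | about 30% |
| mg/kg/h | 1.47 | over 99% |

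The noncentral t distribution with these d values gives 55%, 40% and 29% for the totals, which agrees.

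**4. Power at the protocol's midpoints.** For 7 against 10 mg/kg/h, ignoring Group B's later drop, d = 3 / (CV × √[(7² + 10²)/2]) = 3 / (CV × 8.63). This gives 1.07 at SD 1 h and 0.72 at SD 2 h, with simulated power of about 92% down to 62% on totals.

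**5. Effect of Group B's second phase.** At the midpoints, spending the last 20% of the case at the lower range gives an average of 0.8 × 10 + 0.2 × 5 = 9 mg/kg/h; the last 40% gives 0.6 × 10 + 0.4 × 5 = 8. A separate simulation drew rates uniformly from the stated ranges, with duration CV 20–40% and weight CV 15–20%. Power on totals was 98% down to 66% with no drop, 82% down to 39% with a 20% phase, and 34% down to 14% with a 40% phase. On mg/kg/h it stayed at about 100%.

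**6. Hypotensive episodes.** Simulated Poisson counts, true rate ratio 1.5, mean 5 h, duration CV 20–40%:

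| Base rate | t test on raw count | Rate test with time offset |
|---|---|---|
| 0.5 per h | 54% down to 43% | about 61% |
| 1 per h | 79% down to 59% | 88–89% |

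**7. Type I error.** With no true difference and the same duration distribution in both arms, the raw-count t test rejected in 4.6–5.0% of simulated trials, including runs with extra between-patient variation in the episode rate.

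**8. Chance imbalance in duration.** The standard error of the difference in means is SD × √(2/20) = 0.316 × SD. The 95% range is therefore ±0.62 h at SD 1 h and ±1.24 h at SD 2 h, or 12–25% of a 5 h mean.

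**The case against.** **False positives.** A reader might infer that unequal case length makes the raw comparison produce false positives. The plan does not support that. Allocation is random, so chance differences in duration are already part of the t test's 5% error (step 7). Rejection of 11–17% for raw counts appears only if a shift of 1 to 1.5 h in expected duration is imposed between arms. A chance imbalance of 1.5 h lies outside the 95% range at every SD used, and one of 1 h lies outside it at SD 1 and 1.5 h. Nothing in the documents says that either regimen lengthens surgery.

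**Totals are a legitimate quantity.** Duration is measured after randomisation. If a regimen prolonged anaesthesia, a rate alone would hide the added drug and hypotension burden. This stands: rates should not displace totals.

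**The power contrast is partly built in.** The protocol assigns the mg/kg/h ranges, so testing that rate is in part a check of adherence. The 25% difference and all SDs are assumptions, and at the midpoints before the drop the loss is smaller (step 4). This also stands. It limits how much weight the 99% can bear, but it does not make totals a better scale for comparing doses.

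**Standardising is not trivial.**

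- Weight bears on drug amounts, not on episode counts.
- Ephedrine is given as fixed 5 mg boluses, so per-kg scaling does not suit it.
- An induction bolus of 1.5–2 mg/kg, if counted, precedes the recorded anaesthesia time. It would add 0.3–0.4 mg/kg/h over 5 h but 0.5–0.67 over 3 h, so case length would re-enter.
- One overall rate blends Group B's two phases, and the switch time is not listed as recorded.

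All four stand and shape the fix.

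**The t test is not assigned to each outcome.** Vasopressor use could be read as yes/no and tested by chi-square. That is true, but such a proportion also ignores time at risk.

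**Conclusion.** The point holds as one of precision and interpretability, not of bias or error control. The plan leaves case length and body weight in comparisons of quantities that its own regimens define per kg and per hour.

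Under the assumed spreads, the loss for propofol is large: about 57% down to 30% power on totals for a 25% rate difference. At the protocol's midpoints it is more modest, and it grows with the share of the case that Group B spends in its second phase. For hypotensive episodes the loss is roughly 7 to 30 percentage points at a rate ratio of 1.5 (61 − 54 = 7 at the smallest, 89 − 59 = 30 at the largest).

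The direction follows from the arithmetic. The size rests on duration, weight and rate spreads that the documents do not give. The primary outcome and the sample size are untouched.

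**What to change.** Amend the Measurement tools, Secondary outcome parameters and Statistical analysis sections:

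1. Add body weight, and the time neurophysiology monitoring ends, to the recorded variables.
2. Analyse maintenance propofol as mg/kg/h and fentanyl as mcg/kg/h of anaesthesia. Exclude the induction bolus, or state that it is included. Show Group B's two propofol phases separately.
3. Analyse hypotensive episodes by Poisson regression, or negative binomial if overdispersed, with log anaesthesia duration as offset. Report a rate ratio with 95% CI.
4. Report ephedrine per hour and norepinephrine per kg per hour.
5. Report raw totals and counts beside the rates, with a between-group comparison of surgery and anaesthesia duration, so that any effect of the regimen on case length stays visible.

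The cost is two simple data items and slightly more analysis. Visits, procedures, treatment and sample size do not change.
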